- f) Clinical laboratory tests: (Chemistry) alkaline phosphatase, creatinine, ferritin, C-reactive protein, albumin, alanine aminotransferase, amylase, aspartate aminotransferase, gamma glutamyl transpeptidase, total bilirubin, blood urea nitrogen, glucose, lipase, sodium, potassium, calcium; (Hematology) hemoglobin, hematocrit, red blood cell count, white blood cell count and differential (neutrophils, lymphocytes, monocytes, eosinophils, basophils), platelet count. Only in women who are not WOCBP (to confirm postmenopausal status): follicle stimulating hormone at Visit 0.
- g) Viral screening for human immunodeficiency virus (HIV) 1 or 2, hepatitis B, hepatitis C.
- h) Flexibility for visit days: Visit 3 Day 8±1 d; Visit 4 Day 22±2 d; Visit 5 Day 29±3 d; Visit 6 Day 43±4 d; Visit 7 Day 50±4 d; Visit 8 Day 85±7 d; Visit 9 Day 184±9 d.
- i) Only for the first 6 subjects per group. Questioning on and documentation of AEs as well as systemic and local reactions, the latter in case of upcoming dose decision meetings.
- j) Only IMP-related AEs and any SAEs except proven COVID-19 cases which have to be reported regardless on severity and relatedness to the trial drug until the last scheduled FU Visit as described in Section 10.3.1.9.
- k) Blood draw for anti-SARS-CoV-2 antibodies.
- I) For Cohorts 1 and 8, immunization with at least 1 h intervals between subjects for the first 6 subjects and then with of at least 30 min intervals for the remaining 6 subjects. For all other cohorts and for all boost immunization, the intervals between subjects will be at least 30 min.
- m) Oral swipe for SARS-CoV-2 testing either on Day -1 or at the Visit 1 on Day 1.
- n) The timing of the listed "research" blood draw days may be adapted within the 200 mL maximum volume if justified by the collected data. Leftover blood after completion of the immunogenicity assessments may be used for additional analyses as described in Section 8.7 (Genetics) and/or Section 8.8 (Biomarkers).
- For subjects who have given consent, one aliquot of the blood sample drawn for analysis of CMI may be used for HLA typing to allow additional analysis of T-cell receptor repertoire and/or phenotypic characterization of T cells specific to vaccine-encoded antigens.
- p) If HLA typing using the blood sample collected with Lithium Heparin is not conclusive, EDTA-blood will be drawn for HLA testing.
- q) Only cohorts starting prime dosing after approval of protocol amendment 06.

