#### Clinical Trial Protocol including Amendments Nos. 01 to 09 BNT162-01

Page 25 of 113 Version: 13.0 Date: 12 JAN 2022

Procedure/Assessment	Visit 0	Visit 1 Pre-dose	Visit 1 Dosing & Post-dose	Visit 2 at 24±2 h	Phone call at 48±2 h	Visit 3	Visit 4	Visit 5	Visit 6 (EoT Visit)	Visit 7 (FU Visit)	Visit 8 (FU Visit)
Day *	-30 to 0	1	1	2		8	22	29	43 q	85	184
Collect subject diaries				Х	Х	Х	Х	Х	х		
Record AEs since last visit		Х		Х		Х	Х	Х	х	X n	X n
Local reaction assessment/ systemic events			X d	х		х	x	x			
Concomitant medication r	Х	Х		Х		Х	Х	Х	х	Х	Х
Subject wel being questioning					Хo						

a) Flexibility for visit days: Visit 3 Day 8±1 d; Visit 4 Day 22±2 d; Visit 5 Day 29±3 d; Visit 6 Day 43±4 d; Visit 7 Day 85±7 d; Visit 8 Day 184±9 d.

b) Brief (symptom-directed) physical examination; no height measurement.

c) Vital signs: systolic/diastolic blood pressure, pulse rate, respiratory rate, and body temperature; body weight only Visit 0.

d) At 1, 3, and 6 h (±15 min) after immunization.

e) Urine screening for drugs of abuse (amphetamines, benzodiazepines, barbiturates, cocaine, cannabinoids, opiates, methadone, methamphetamines, phencyclidine, tricyclic antidepressants).

- f) Dipstick urine analysis: glucose, bilirubin, ketone, specific gravity, blood, pH, protein, urobilinogen, nitrite, and leukocytes. Microscopic urinalysis: if warranted by dipstick results, urine sediment will be microscopically examined for the presence of red blood cells, white blood cells, casts, crystals, epithelial cells, and bacteria.
- g) Clinical laboratory tests: (Chemistry) alkaline phosphatase, creatinine, ferritin, C-reactive protein, albumin, alanine aminotransferase, amylase, aspartate aminotransferase, gamma glutamyl transpeptidase, total bilirubin, blood urea nitrogen, glucose, lipase, sodium, potassium, calcium; (Hematology) hemoglobin, hematocrit, red blood cell count, white blood cell count and differential (neutrophils, lymphocytes, monocytes, eosinophils, basophils), platelet count. Only in women who are not WOCBP (to confirm postmenopausal status): follicle stimulating hormone at Visit 0.
- h) Viral screening for human immunodeficiency virus (HIV) 1 or 2, hepatitis B, hepatitis C.
- i) Blood draw for anti-SARS-CoV-2 antibodies.
- j) Oral swipe for SARS-CoV-2 testing either on Day -1 or at the Visit 1 on Day 1.

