- f) Clinical laboratory tests: (Chemistry) alkaline phosphatase, creatinine, ferritin, C-reactive protein, albumin, alanine aminotransferase, amylase, aspartate aminotransferase, gamma glutamyl transpeptidase, total bilirubin, blood urea nitrogen, glucose, lipase, sodium, potassium, calcium; (Hematology) hemoglobin, hematocrit, red blood cell count, white blood cell count and differential (neutrophils, lymphocytes, monocytes, eosinophils, basophils), platelet count. Only in women who are not WOCBP (to confirm postmenopausal status): follicle stimulating hormone at Visit 0.
- g) Viral screening for human immunodeficiency virus (HIV) 1 or 2, hepatitis B, hepatitis C.
- h) Flexibility for visit days: Visit 3 Day 8±1 d; Visit 4 Day 22±2 d; Visit 5 Day 29±3 d; Visit 5a Day 36±3 d; Visit 6 Day 43±4 d; Visit 7 Day 50±4 d; Visit 8 Day 85±7 d; Visit 9 Day 184±9 d; Visit 10 Day 365±14 d; Visit 11 Day 547±14 d; Visit 12 Day 730±14 d.
- i) Only for HIV-positive subjects (done locally).
- j) Visits 8 and 9, only IMP-related AEs and any SAEs. Visits 10, 11, and 12, only any SAEs except proven COVID-19 cases which have to be reported regardless on severity and relatedness to the trial drug until the last scheduled FU Visit as described in Section 10.3.1.9. For subjects who receive non-trial SARS-CoV-2 vaccinations, the AEs expected to be captured after these vaccinations are within the frame of post-marketing safety data reporting (see Section 8.3.1).
- k) Blood draw for anti-SARS-CoV-2 antibodies.
- I) For first immunization in Cohort 13, immunization with at least 30 min intervals between the primary immunizations and 30 min between the boost immunizations. For Cohorts 11 and 12, the interval between the trial subjects will be at least 15 min for the prime immunizations and at least 5 min for the boost immunizations.
- m) Oral swipe for SARS-CoV-2 testing either on Day -1 or at the Visit 1 on Day 1.
- n) The timing of the listed "research" blood draw days may be adapted (within the 200 mL maximum volume) if justified by the collected data. Leftover blood after completion of the immunogenicity assessments may be used for additional analyses as described in Section 8.7 (Genetics) and/or Section 8.8 (Biomarkers). For subjects who receive non-trial SARS-CoV-2 vaccinations, there will be no blood sampling for immunogenicity or cell-mediated immune testing in the FU Visits.

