# 8.3.1 Time period and frequency for collecting AE and SAE information

For Cohorts 1 to 10, all AEs and SAEs will be collected from the date of subject consent until discharge from the trial only IMP-related AEs and any SAEs will be collected.

For Cohorts 11 to 13 and 14, all AEs and SAEs will be collected from the date of subject consent until Visit 7 (the EoT Visit). From Visit 7 through 9 only IMP-related AEs, SAEs, and SARS-CoV-2 infections will be collected. After Visit 9 (e.g., Visits 10, 11, and 12) until the last scheduled FU Visit (i.e., when the subject is discharged from the trial), any SARS-CoV-2 infections and SAEs will be collected.

For subjects in Cohorts 11 to 13 who receive a non-trial SARS-CoV-2 vaccination, AEs/SAEs will be collected as specified above until the date when the subject was vaccinated with the non-trial SARS-CoV-2 vaccine. The AEs expected to be captured after non-trial SARS-CoV-2 vaccination are within the frame of post-marketing safety data reporting.

All SAEs (initial and follow-up reports) will be recorded and reported to the sponsor or designee within 24 h after becoming aware of the event, as indicated in Section 10.3.1.10.

Investigators are not obligated to actively seek AEs or SAEs after conclusion of the trial participation. However, if the investigator learns of any SAE, including a death, at any time after a trial subject has been discharged from the trial, and he/she considers the event to be reasonably related to the IMP administration or trial participation, the investigator must promptly notify the sponsor.

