#### 6.4.3. Adverse Events

#### Definition

For detailed information on adverse events see section 10.3 of the protocol.

Adverse events (AEs) will be coded using the Updated Version MedDRA® 23.0 including specific terms for COVID-19 to get a system organ class (SOC) and preferred term (PT) for each AE.

A treatment emergent adverse event (TEAE) is defined as any AE with an onset after the first immunization (if the AE was absent before the first immunization) or worsened after the first immunization (if the AE was present before the first immunization). AEs with an onset date more than 28 days after the last immunization will be considered as treatment emergent only if assessed as related to IMP by the investigator. AEs that cannot be determined to not be treatment emergent due to missing date or time will be defined as TEAE.

Clarification: To clarify the definition in the protocol, AEs with an onset date at the date of the first immunization will only be considered as treatment emergent if the AE occurred after the first immunization.

The TEAEs will be evaluated for the following time intervals, clarifying and harmonizing the intervals defined in the protocol:

- Prime immunization up to boost immunization or day 28 (inclusive) after initial immunization (whatever comes first)
- Boost immunization up to day 28 (inclusive) after boost immunization
- All TEAEs (regardless of relationship assessment) occurring from

- Prime immunization up to day 28 after boost immunization (inclusive).
- If no boost immunization, up to 28 days (inclusive) after prime immunization
- All TEAEs assessed as related through visit 10.

The intervals starting or ending with an immunization, will start or end with the date and time of the immunization. TEAEs are assigned to the time intervals according to their start date and time. AEs with missing date will be assigned to each of the respective intervals if it cannot be ruled out, that it belongs to the time interval.

Deviating from the protocol, the time intervals including 7 days after each immunization will not be analyzed.

AEs will be evaluated for the following time interval 'After Day 28 after boost or after prime (if no boost)':

All AEs (regardless of relationship assessment) occurring

- After day 28 after boost immunization
- o If no boost immunization, after 28 days after prime immunization

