## 7. Supporting Documentation

## 7.1. Appendix 1: Changes to Protocol-Planned Analyses

• The primary endpoint defined in the protocol on page 48 'The proportion of subjects with at least 1 unsolicited TEAE:

o For BNT162a1, BNT162b1, BNT162b2, and BNT162c2 (P/B): occurring up to 21 d after the prime immunization (trial day 22) and 28 d after the boost immunization (trial day 50).'

will be changed for consistency to

'The proportion of subjects with at least 1 unsolicited TEAE occurring after prime immunization up to boost immunization or 28 days after prime immunization (whichever comes first) and 28 d after the boost immunization.'

- The time intervals from each immunization up to (and including) 7 days after each immunization will not be analyzed separately for AEs.
- All TEAEs assessed as related through visit 10 are included in the overall time interval.
- In protocol section 9.4.2 it is stated "For each injection, the number and percentage of subjects reporting at least one local reaction or systemic reaction (i.e., solicited data collected using subject diaries) will be summarized for each of the following types using the Safety Set:
  - Any local reactions or systemic reactions
  - Grade  $\geq$ 3 local reactions or systemic reactions".

However, for each injection, the number and percentage of subjects reporting at least one local reaction or systemic reaction (i.e., solicited data collected using subject diaries) will be summarized for any local or systemic reactions as well as worst type of local or systemic reaction. No summary of grade  $\geq 3$  local reactions or systemic reactions will be presented.

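### In Cohorts 11-13, a related SAE starting after Visit 10 is a TEAE by the SAP's definition but falls in no TEAE interval, so the TEAE tables omit it

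*SAP*

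**What the plan says.** **Definition.** SAP 6.4.3 states that "AEs with an onset date more than 28 days after the last immunization will be considered as treatment emergent only if assessed as related" to the vaccine. It gives no latest onset date. Protocol 10.3.1 defines a TEAE in the same way.

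**Interval.** Among the TEAE intervals in SAP 6.4.3, the only one that reaches beyond day 28 after the last dose does so through the item "All TEAEs assessed as related through visit 10". SAP Appendix 1 (section 7.1) confirms where these events belong: "All TEAEs assessed as related through visit 10 are included in the overall time interval".

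**Visit schedule.** For Cohorts 11-13, the visit-window footnote to protocol Table 8 gives "Visit 10 Day 365±14 d; Visit 11 Day 547±14 d; Visit 12 Day 730±14 d". The other schedules stop earlier. Table 6 (prime/boost dose ranging) ends with "Visit 8 Day 85±7 d; Visit 9 Day 184±9 d" and Table 7 (BNT162c2 single dose) with "Visit 7 Day 85±7 d; Visit 8 Day 184±9 d". Table 9 (Cohort 14) also ends at Visit 9, Day 184.

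**Collection.** For Cohorts 11-13, the AE footnote to protocol Table 8 says "Visits 8 and 9, only IMP-related AEs and any SAEs. Visits 10, 11, and 12, only any SAEs", with proven COVID-19 cases reported in any event. Protocol 8.3.1 agrees that after Visit 9, up to the last scheduled follow-up visit, "any SARS-CoV-2 infections and SAEs will be collected".

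**The concern.** The definition and the interval sit in the same SAP section and disagree. The definition is open-ended. The interval closes at a visit that is not a collection boundary: in Cohorts 11-13, non-serious related AEs stop being collected at Visit 9 and SAEs at Visit 12. The SAP gives no reason for choosing Visit 10.

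What is at stake is whether the safety tables agree with each other. SAP 6.4.3 produces the TEAE tables by defined interval: the overall summary, treatment-emergent AESIs, the SOC/PT tables (including related serious events and those with unresolved, fatal or unknown outcome) and worst grade. An event outside every interval appears in none of them. The related-TESAE row could show no late event while the post-day-28 AE summary shows one.

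**Working it through.** The point needs a comparison of passages and some counting. The plan has no figure to reproduce.

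**1. Follow one event through the plan.** Take a subject in Cohort 12 who has had both doses and no non-trial vaccination. A related SAE starts between Visit 10 (Day 365) and Visit 11 (Day 547).

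| Step | Source | Result |
|---|---|---|
| Is it collected? | Protocol Table 8 AE footnote; 8.3.1 | Yes, SAEs run to Visit 12 |
| Is it a TEAE? | SAP 6.4.3 definition | Yes, it is related and there is no end date |
| Prime-to-boost interval? | SAP 6.4.3 | No |
| Boost to day 28 after boost? | SAP 6.4.3 | No |
| Overall interval? | SAP 6.4.3; Appendix 1 | No, related events stop at Visit 10 |
| TEAE/TESAE, AESI, SOC/PT, worst-grade tables? | SAP 6.4.3, by interval | Absent |
| AE summary after day 28? | SAP 6.4.3, AEs | Present: SAE and related-SAE rows, no upper limit |
| Listings? | SAP 6.4.3, AE listings | Present |

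The post-day-28 summary has no SOC/PT breakdown and no AESI row. AESIs are summarized only as treatment-emergent AESIs by interval, so a serious related AESI after Visit 10 would enter no AESI summary.

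**2. Who can be affected.** From protocol Table 5:

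- Planned subjects: 72 + 120 + 290 + 72 + 84 = 638.
- Planned cohorts: 6 + 10 + 14 + 6 + 7 = 43.
- With a Visit 10 (Cohorts 11-13): 30 + 90 + 30 = 150 subjects in 3 cohorts.
- Without: 638 − 150 = 488 subjects (76%) in 43 − 3 = 40 cohorts (93%).

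In those 40 cohorts scheduled follow-up ends at about Day 184. A bound later than the last visit excludes nothing, so none of their events is lost.

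**3. Time left outside the interval in Cohorts 11-13.** 730 − 365 = 365 scheduled days, and 365/(730 − 1) = 50% of Days 1 to 730.

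**4. Effect of a corrected bound on comparability.** The present bound sets about Day 184 beside Day 365, a gap of 365 − 184 = 181 days. Running to the last visit sets Day 184 beside Day 730, a gap of 730 − 184 = 546 days. The correction makes follow-up within the overall column more unequal, which has to be disclosed.

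**The case against.** The best defence has five parts.

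- **The event is still reported.** The post-day-28 summary gives the number and percentage of subjects and the number of events, with separate rows for SAEs, related SAEs, related grade 3 or higher AEs, and deaths. The listings are complete. This stands. A reader might infer that late related SAEs vanish from the report, and the documents do not support that.
- **Most cohorts are untouched.** A reader might infer that a cut-off missing from 40 of 43 cohorts damages all of them. It does not: the wording has no meaning there, but no event is excluded.
- **The exposed group is smaller than 150.** The synopsis says approval of a third dose has affected the two-year follow-up. Protocol 7.2 discontinues subjects in Cohorts 11-13 who receive a non-trial SARS-CoV-2 vaccine, 8.3.1 ends their AE collection at that date, and SAP 6.1 excludes later data. Protocol 4.4 even foresees ending early if nobody remains. This stands: 150 is a ceiling, and the documents do not say how many remain after Day 365.
- **No primary endpoint moves.** The unsolicited-TEAE endpoint ends 28 days after the boost, and the trial tests no hypothesis. This stands.
- **The bound is declared and widens coverage.** The longest AE interval in protocol 9.4.2 ends 28 days after the last dose, and Appendix 1 lists the extension openly. This is true but does not resolve the mismatch: the definition was left open-ended and no reason is given for stopping at Visit 10. The version 5 entry in the SAP history says that late related TEAEs are to fall in one of the analyzed intervals and names no visit limit. That is a sign of intent, not a discrepancy in itself.

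**Conclusion.** The point holds in a narrow form. Followed as written, the SAP classes a related SAE starting after Visit 10 in Cohorts 11-13 as a TEAE and then leaves it out of every TEAE table. The affected period is 365 scheduled days. The affected group is at most 150 subjects and probably fewer. Few events are to be expected, but any that occur would be late, serious and judged related. The consequence is an incomplete set of TEAE, TESAE and AESI tables that could disagree with the post-day-28 AE summary. No data are lost and no primary result changes.

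This rests on two readings: that the TEAE tables are produced only for the intervals listed in SAP 6.4.3, and that the Visit 10 limit applies to the overall interval, as Appendix 1 states.

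**What to change.** In SAP 6.4.3 and in Appendix 1, replace the Visit 10 limit with: *through the last scheduled follow-up visit of the cohort*.

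Add a footnote to the overall-interval tables stating that:

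- follow-up differs by cohort, ending at about Day 184 in Cohorts 1-10 and 14 and running up to Day 730 in Cohorts 11-13;
- in Cohorts 11-13, non-serious related AEs were collected only to Visit 9, except proven COVID-19 cases, which are recorded to the last follow-up visit (protocol Table 8, 8.3.1 and 10.3.1.9).

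The cost is two SAP sentences, one footnote and one date window in the TEAE programs, with no new data. The downside is the wider spread of follow-up within the overall column (a gap of 546 rather than 181 days), which the footnote discloses but does not remove.

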# 10.3 Adverse events: Definitions and procedures for recording, evaluating, follow-up, and reporting

# 10.3.1 Definition of AE and TEAE

• An AE is any untoward medical occurrence in a patient or clinical study participant, temporally associated with the use of study intervention, whether or not considered related to the study intervention.

NOTE: An AE can therefore be any unfavorable and unintended sign (including an abnormal laboratory finding that is clinically significant), symptom, or disease (new or exacerbated) temporally associated with the use of study intervention.

- Events after signing ICF and before IMP administration will be handled as AEs.
- A TEAE is defined as any AE with an onset date on or after the first administration
  of IMP (if the AE was absent before the first administration of IMP) or worsened
  after the first administration of IMP (if the AE was present before the first
  administration of IMP). AEs with an onset date more than 28 d after the last
  administration of IMP will be considered as treatment-emergent only if assessed as
  related to IMP by the investigator.

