# 10.3.1.7 Recording and follow-up of AE and/or SAE

## AE and SAE recording

The investigator needs to assess and document any AE regardless of association with the use of the trial treatment during the period of observation (starting from Visit 0 until 21 d after the last immunization or trial subject discharge from the trial, whichever one is later). To ensure trial subject safety during the trial, safety will be monitored from Visit 0 (screening) until at least (approximately) 6 months after the last immunization.

BioNTech SE
Confidential

- Data pertaining to AEs will be collected during each trial visit either based on the trial subject's spontaneous description or investigator's inquiry or discovered in the course of examinations done during the visit, clinical significance of any sign or symptom needs to be evaluated by the investigator.
- Clinically significant findings need to be documented as AEs in the source data and CRF. Findings that are evaluated and documented in the source data as not clinically significant (e.g., an abnormal laboratory value without any clinical manifestation), should not be documented as AE.
- The investigator will then record all relevant AE information in the CRF and perform an assessment on:
  - Intensity, see the section "Assessment of intensity" in Section 10.3.1.11 for guidance on the assessment of intensity
  - Seriousness
  - Outcome
  - Causal relationship of the AE to the trial treatment
  - Any trial treatment action and/or any other action taken
- All assessments as well as AE term (diagnosis/description), start date and time of onset, end date and time need to be documented in the CRF.
- There may be instances when copies of medical records for certain cases are requested by the sponsor. In this case, all trial subject identifiers, with the exception of the trial subject number, will be redacted on the copies of the medical records before submission to the sponsor.
- To avoid colloquial expressions, the AE should be reported in standard medical terminology. The investigator will attempt to establish a diagnosis of the event based on signs, symptoms, and/or other clinical information. Whenever possible, the diagnosis (not the individual signs/symptoms) will be documented as the AE. If a definitive diagnosis is not possible, the individual signs and symptoms should be recorded.

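### SAP 6.4.3 counts a worsened pre-dose AE as treatment-emergent, but if it stays in one record the start-date rule keeps it out of the prime and boost intervals

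*SAP*

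**What the plan says.** The TEAE definition in SAP 6.4.3 has two limbs. One is new onset after the first immunization. The other covers an AE that "worsened after the first immunization (if the AE was present before the first immunization"). Protocol 10.3.1 has the same two limbs.

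For tabulation, SAP 6.4.3 gives one rule: "TEAEs are assigned to the time intervals according to their start date and time". On the bounds it says: "The intervals starting or ending with an immunization, will start or end with the date and time of the immunization". The listed intervals are prime to boost (or day 28 if earlier), boost to day 28 after boost, and an overall interval from prime to day 28 after the last dose. The overall interval has one addition, "All TEAEs assessed as related through visit 10", and SAP Appendix 1 repeats it: "All TEAEs assessed as related through visit 10 are included in the overall time interval". AEs with a missing date go to every interval that remains possible.

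On data capture, Protocol 10.3.1 says: "Events after signing ICF and before IMP administration will be handled as AEs". Protocol 8.3.1 collects AEs from consent, and screening runs from Day -30 (Protocol Tables 6 to 9). For each AE, Protocol 10.3.1.7 requires that "start date and time of onset, end date and time need to be documented in the CRF"; it lists no date of a grade change.

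**The concern.** An AE in the worsening limb begins, by definition, before the first dose. If its only date is the onset date, the assignment rule places it ahead of the opening of both the prime and the boost interval. One sentence of SAP 6.4.3 admits the event as a TEAE and a later one leaves it without a place in either.

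The proportion of subjects with at least one unsolicited TEAE is a primary endpoint, and SAP 1.1 defines it by those two intervals. The summaries by SOC and PT, the worst-grade tables and the figures are also produced per interval. The result could therefore depend on whether a site opened a new record when an AE worsened or edited the existing one. The outcome also sits oddly beside the missing-date rule: an AE without a date may be counted in several intervals, while a fully dated worsened AE may be counted in neither dose interval.

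**Working it through.** **The plan's own figures.** The documents give no figure for this rule. The only design figures are in Protocol Table 10, from 1 - (1 - p)^n. They reproduce: n = 12, p = 15% gives 85.8%; n = 30, p = 5% gives 78.5%; n = 90, p = 5% gives 99.0%. Nothing below changes them.

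**Applying the interval rules.** Set the prime at t = 0 d and the boost at t = 21 d, so the overall interval closes at t = 21 + 28 = 49 d. The prime interval is then 0 to 21 and the boost interval 21 to 49. I read the addition for related TEAEs as having no lower date bound, because none is written. Take an AE with onset at t = -5:

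| Worsens at | Assessed as | One record, original start date | Date of worsening, or a new record |
|---|---|---|---|
| t = 3 | unrelated | no interval | prime and overall |
| t = 3 | related | overall only | prime and overall |
| t = 24 | unrelated | no interval | boost and overall |
| t = 24 | related | overall only | boost and overall |

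The separate AE table in SAP 6.4.3 for events after day 28 does not catch the unrelated cases either, because it too assigns by start date. They remain only in the listing of all AEs.

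**Which record would it be?** The protocol points both ways.

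- Towards one record: Section 8.3.3 puts new or updated information in the CRF entry already completed, and Section 10.3.1.7 asks for onset and end dates.
- Towards a separate record: Section 10.3.1.1 lets the investigator report a worsened pre-existing condition as an AE, and the Outcome part of Section 10.3.1.7 speaks of AEs documented as a worsening of a baseline condition. Such a record would start after the dose and fall in the right interval.

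No section requires a new record on worsening.

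**Size per affected subject.** If the omitted event is the subject's only counted unsolicited TEAE in the interval, the reported proportion falls by 1/n:

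- 1/12 = 8.3 percentage points (dose-ranging cohorts)
- 1/20 = 5.0 (Cohort 14)
- 1/30 = 3.3 (Cohorts 11 and 13)
- 1/90 = 1.1 (Cohort 12)

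If the subject has another counted unsolicited TEAE in that interval, the proportion does not change.

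**How often.** The documents give no frequency. For an assumed share w of subjects with such an event, the chance of at least one in a cohort is 1 - (1 - w)^n:

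| Assumed w | n = 12 | n = 30 | n = 90 |
|---|---|---|---|
| 1% | 11.4% | 26.0% | 59.5% |
| 2% | 21.5% | 45.5% | 83.8% |
| 5% | 46.0% | 78.5% | 99.0% |
| 10% | 71.8% | 95.8% | >99.9% |

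These are chances that such an event exists in the cohort. The chance that a reported proportion changes is lower, since that also needs a single record and no other counted TEAE.

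**The case against.** The strongest reply is that the protocol already treats a worsening as an AE in its own right. Its rule that a documented worsening has recovered once the condition is back at baseline status makes most sense if the worsening has its own record. This stands for worsened medical history, and it narrows the exposed group to AEs that began between consent and the first dose, were still ongoing, worsened afterwards and were kept as one record. Exclusion criterion 1 (Protocol 5.2.1) narrows it further by excluding acute illness in the 72 h before the first immunization. It does not empty the group, because an illness that has nearly resolved is allowed.

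The analysis is also purely descriptive, and dose decisions rest on Safety Review Committee review of early safety data, so these tables drive no decision rule. That stands too, and it bears on the weight of the point. It does not answer the mismatch, because reporting a worsening as an AE is left to the investigator and no section requires a new record.

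A reader might infer that the worsening limb is never counted at all. The documents do not support that: a separate record is counted correctly, related TEAEs enter the overall interval, and all AEs are listed. A reader might also infer that worsening after the boost is wrongly credited to the prime. That cannot apply to an AE with pre-dose onset, which enters neither interval. It describes an AE that starts between the doses and is kept as one record. Assigning that AE by onset is a choice the SAP states openly, and it is still counted in the prime and overall intervals.

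**Conclusion.** The definition and the assignment rule in SAP 6.4.3 do not fit together for an AE with pre-dose onset that worsens after dosing and stays in its original record. Such an event is absent from both intervals that define the primary unsolicited-TEAE proportion. If unrelated, it is absent from every TEAE table; if related, it is in the overall interval only.

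The effect on a reported proportion is at most 1/n per affected subject. It would be wrong to infer that every affected subject moves the proportion by that amount. The conclusion rests on the worsening being kept in the original record, which the documents leave open, and on reading the related-TEAE addition as having no lower bound. The number of affected subjects is unknown and probably small. Solicited reactions, sample size and dose decisions are untouched. This is a minor correction to the SAP.

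**What to change.** Add to SAP 6.4.3, after the assignment rule: *A TEAE that qualifies because an AE with onset before the first immunization worsened after it is assigned to the interval containing the date of worsening or, if the worsening has a separate record, the start date of that record. If this date is unavailable, the TEAE is assigned to each interval that remains possible.* The fallback is the one the SAP already uses for missing dates.

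Before database lock, query AEs ongoing at the first dose for whether and when they worsened.

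The cost is one SAP sentence and a small query round. Because the date of a grade change is not among the AE data that Protocol 10.3.1.7 requires, some sites may be unable to supply it. Those events would then follow the fallback and could appear under both the prime and the boost. The rule for AEs that start between the doses can stay as it is.
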